4.4 Randomization and Blinding

NA.

4.5 Sample Size Determination

Sample size has not been determined based upon statistical calculations. The sample size of up to approximately 16 patients, with approximately 4 patients per cohort, was chosen based on scientific judgment to have sufficient replication to meet the study objectives.

The best efforts will be made to enrol at least 1 patient of each gender in each cohort of 4.

5 Considerations for Statistical Analysis

The SAS Viya 3.5 (or higher) will be used for all analysis, unless otherwise specified.

5.1 Analysis Periods

Analysis Periods

When Visit data is to be displayed, the following abbreviations in the 'Table Display' column will be used for Tables, Figures and Listings (TFL):

Table 1: Visit and study periods

Visit Number	Study Period (Day or Month)	Table Display
Screening V1A	Minimum 6 to 8 weeks before Screening V2	SCR1
Screening V1B	Day -49 to Day -14	SCR2
Baseline V2	Day -7	BAS D-7
Baseline V3	Day -3	BAS D-3
Baseline V4	Day -2	BAS D-2
Baseline V5	Day -1	BAS D-1
Treatment V6	Day 1	TRT
Follow-up V7	Day 2	FUP D2
Follow-up V8	Week 2	FUP W2
Follow-up V9	Week 3	FUP W3
Follow-up V10	Week 4	FUP W4
Follow-up V11 to V17*	Week 4 to Week 7	FUP W4 to W7
Follow-up V18	Week 8	FUP W8
Follow-up V19 to V25*	Week 8 to Week 11	FUP W8 to W11
Follow-up V26 to V29*	Week 12	FUP W12
Follow-up V30 and V31	Week 12 to Week 13	FUP W12 and FUP W13
Follow-up V32	Week 14	FUP W14
Follow-up V33	Week 15	FUP W15
Follow-up V34	Week 16	FUP W16
Follow-up V35	Week 20	FUP W20
Follow-up V36	Week 24	FUP W24
Follow-up V37	Week 28	FUP W28
Follow-up V38	Week 32	FUP W32
Follow-up V39 to V42*	Week 36	FUP W36

Sponsor: Vivet Therapeutics, SAS
Protocol: VTX-801_CLN_001
SAP: 1.0 / 24Jan2025

Follow-up V43	Week 38	FUP W38
Follow-up V44	Week 40	FUP W40
Follow-up V45	Week 44	FUP W44
Follow-up V46	Week 52	FUP W52
Follow-up V47	Month 15	FUP M15
Follow-up V48	Month 18	FUP M18
Follow-up V49	Month 21	FUP M21
Follow-up V50	Month 24	FUP M24
End of Study	End Of Study Visit	EOS
FUP (safety) call	Phone call following treatment early termination	FUP call

*Multiple assessments within a given visit will be averaged for summary tables, and individual assessments will be provided in listings.

For visits where assessments occur at multiple timepoints within a visit (e.g. Radiocopper Assessments), the appropriate timepoint description will be added in the format Visit – Timepoint (e.g. Treatment – 4 hours post-dose).

Visit Windowing

All data will be analyzed according to the planned visit as collected in the eCRF.

Unscheduled visits

All data from unscheduled visits will not be included in summaries and will only be presented in data listings, if not otherwise specified.

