5.3 Data Derivations

Baseline and Change from Baseline

Baseline and change from baseline will be calculated for all assessments, including additional assessments (if applicable), as follows:

- Baseline value is defined as the last available value prior VTX-801 dosing, if not defined otherwise in the study protocol. Assessments that occurred on the same day as VTX-801 dosing, when time of assessment is not available, will be assumed to be prior to VTX-801 dosing (unless the assessment is planned after VTX-801 dosing in the study protocol).
- Change from baseline will be calculated for any post-baseline data as the difference between the post-baseline assessment value and the baseline value.

Study Day

Study day will be calculated as (assessment/sample date – date of first study treatment dose) for pre-baseline assessments and [(assessment/sample date – date of first study treatment dose) + 1] for post-baseline assessments, i.e., there will be no study day 0 and study day 1 will correspond to the first study treatment dose.

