7.9.2 Clinical Laboratory Evaluation

All laboratory data collected will be reported using standards units.

Sponsor: Vivet Therapeutics, SAS
Protocol: VTX-801_CLN_001
SAP: 1.0 / 24Jan2025

The continuous numerical measurements of all laboratory tests will be summarized using descriptive summary statistics for each visit, by dose cohort and overall. A listing of laboratory parameters will be created.

Also, results of pregnancy tests will be listed.

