7.9.4 Other Safety Data

Electrocardiogram (ECG)

All ECG parameters collected will be reported.

The numerical measurements and change from baseline of ECG parameters will be summarized by timepoint using descriptive summary statistics for each visit, by dose cohort and overall. ECG parameters will also be provided in a listing.

Ophthalmology

A listing of all ophthalmological examination assessments will be created on the SAF.

Sirolimus

Sirolimus assessments will be reported in listings on the SAF.

Radiocopper administration

Radiocopper administration will be reported in a listing on the SAF.

Steroids:

Per protocol steroid treatments will be reported in a listing on the SAF.

[REDACTED]

[REDACTED].

Vector shedding:

Vector shedding findings will be reported in a listing on the SAF.

Brain and abdominal MRI:

Brain and abdominal MRI assessments/findings will be reported in a listing on the SAF.

Physical examination:

Physical Examination includes the following parameters: General appearance, Skin, Head and neck, Eyes, ears, nose, throat, Lymph node palpation, Lungs, Chest, Abdomen, Extremities, Neurological function.

A listing of physical examination evaluations will be created on the SAF.

8 Interim Analysis (IA)

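### SAP 7.9.2 omits the protocol's CTCAE-graded and change-from-baseline laboratory summaries without declaring it, and SAP 5.1 leaves open whether a short liver-enzyme rise would show in the tables

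*SAP*

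**What the plan says.** **Laboratory outputs.** SAP 7.9.2 says "All laboratory data collected will be reported using standards units" and "The continuous numerical measurements of all laboratory tests will be summarized using descriptive summary statistics for each visit, by dose cohort and overall". It adds a listing and the pregnancy tests, and names no laboratory source. On change from baseline, SAP 5.3 says "Baseline and change from baseline will be calculated for all assessments", but the only summary of it in the safety sections is for ECG (SAP 7.9.4): "The numerical measurements and change from baseline of ECG parameters will be summarized by timepoint".

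**Protocol requirement.** Protocol 11.4.4.2 asks for descriptive statistics on central laboratory data, summaries of values and of change from baseline, a summary of CTCAE v5 graded abnormalities with transaminases named, and shift tables. The footnote to Table 10 in Protocol 8.1.12 also makes central liver results the ones analysed. SAP Section 9 lists changes from the protocol; its one entry on laboratory evaluations is that shift tables are dropped.

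**Visits.** SAP 5.1 says "All data from unscheduled visits will not be included in summaries and will only be presented in data listings", unless specified otherwise, and 7.9.2 does not specify otherwise. The SAP's visit table puts V11-V17 and V19-V25 in one starred row each (V26-V29 and V39-V42 are starred too), with the footnote "Multiple assessments within a given visit will be averaged for summary tables, and individual assessments will be provided in listings". The V30/V31 row has no star and keeps two labels, "FUP W12 and FUP W13". The same section says "All data will be analyzed according to the planned visit as collected in the eCRF".

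**The concern.** Laboratory change is part of the primary endpoint, and SAP 8.1 describes an abbreviated report focused on safety. Protocol 9.2.4 keeps abnormal laboratory values out of routine adverse-event reporting on the ground that they are analysed separately. The laboratory tables are that separate analysis.

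By-visit means and medians are poor at showing one patient's brief peak; a graded summary is the output that shows it. Protocol 7.5.2.1 expects unscheduled samples because nobody can predict when transaminases will rise, and Protocol 10.5.3 raises liver testing to twice weekly from Week 4 to Week 12 after dosing. If the graded summary is missing, unscheduled results are listed only, and the twice-weekly panels may be averaged together or absent, the tables could look flat for a patient whose enzymes briefly rose.

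**Working it through.** **1. Required against specified**

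| Protocol 11.4.4.2 | SAP 7.9.2 | Declared in SAP Section 9 |
|---|---|---|
| Descriptive statistics of values | Yes, by visit | not needed |
| Change-from-baseline summary | Not specified (derived under 5.3) | No |
| CTCAE-graded abnormality summary | Not specified | No |
| Shift tables | Not specified | Yes |

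Of three protocol outputs absent from 7.9.2, one is declared.

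**2. How many liver panels are involved**

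Inputs are the blood volumes in Protocol Table 18 (Section 17.1.2), at 5 mL per panel.

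- Local row: V2, V7, V8, V9, V10, V18, V26 and a second Week 12 sample make 8 panels. Adding 7 (V11-V17) and 7 (V19-V25) gives 22, and 22 x 5 = 110 mL, which is the table's total. Without V2, 21 are post-dose.
- Central row: 25 / 5 = 5 panels (V2, V8, V10, V18, V26), so 4 are post-dose.
- Occasions with no planned central tube: 21 - 4 = 17.
- Of those 17, the home-nurse visits are V9, V11-V17 and V19-V25: 1 + 7 + 7 = 15. The protocol's visit tables label these panels Local. Section 10 sends home-nurse samples to the central laboratory by default, while Sections 10.3 and 12.1.3 only permit it.
- If the default is followed, 17 - 15 = 2 occasions lack a central result: V7 and the second Week 12 sample. (Table 18 puts that sample at V29, an expansion-cohort visit. For the dosed cohorts it falls at V28 or V30. V30 is a home visit, which would leave 1.)

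The range is therefore about 2 to 17 of 21.

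In Weeks 4-12 there are 1 + 7 + 1 + 7 + 2 = 18 occasions, which equals 9 weeks x 2. The two seven-visit rows hold 14 of them (78%).

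**3. What row averaging would do**

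With *m* of 7 panels at *p* times ULN and the rest at 1x, the row value is (7 - m + m x p) / 7. The example is an isolated AST of 4.9x ULN, just under the stand-alone 5x criterion in Protocol 6.3.

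- One panel at 4.9x: (6 + 4.9) / 7 = 1.56x.
- Two panels at 4.9x: (5 + 9.8) / 7 = 2.11x.
- Rise and fall of 2x, 4.9x, 2x with four at 1x: (4 + 2 + 4.9 + 2) / 7 = 1.84x.
- One panel at 4.9x with the other six at 2x: (12 + 4.9) / 7 = 2.41x.

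Averaging comes before summarising, so the maximum column is a maximum of patient averages. In a cohort of 2 with one patient flat at 1x and the other as in the first line, the row shows mean (1.56 + 1) / 2 = 1.28x and maximum 1.56x.

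**4. Which reading of the footnote**

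- Whole row: stars appear only on rows that pool visit numbers under one label. V11-V17 and V19-V25 hold one planned panel per visit, so averaging inside a visit would do nothing there. Vital signs are only listed (SAP 7.9.3), so the liver panel is the one tabulated measurement those rows could hold.
- Single visit: the footnote speaks of a given visit, analysis follows the planned visit, and V11 to V17 are seven planned visits.

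The text does not settle it. Nor do points 2 and 3 add up: a panel left out as local is absent, not diluted.

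**The case against.** The case against is substantial.

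- *The protocol already names the source.* It does, twice: central. A central-only table is the protocol's design and not a SAP error. What stands is that the SAP does not repeat the rule, and that the protocol is unclear on where home-nurse samples go.
- *Listing unscheduled tests separately is ordinary practice.* True for a by-visit table, which has no row for them. It leaves a gap here only because the graded summary, which could have included them, is also missing.
- *The TFL shells may contain the missing tables, and Protocol 11.5 lets the study report document changes.* Both are possible; the shells are a separate document. So a reader should not conclude that the omission will never be declared. Neither point puts the graded summary back into the plan.
- *Other outputs catch the events that matter.* Largely true. ALT of at least 1.5x baseline is an event of special interest (Protocol 9.6), entered as an adverse event from Week 2 to Month 9 (7.5.2.2). ALT or AST of at least 5x ULN meets a DILI criterion (6.3). SAP 7.9.1 counts special-interest events, liver events and events meeting a stopping rule. Clinically significant values must be reported as adverse events (Protocol 9.2.4).

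A reader might infer that the SAP definitely averages seven panels into one, or that 17 of 21 liver results are lost to the analysis. The documents support neither. The first is one of two available readings; the second is the upper end of a range that starts near 2.

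**Conclusion.** The firm part does not depend on any reading. The SAP specifies neither the graded laboratory summary nor the laboratory change-from-baseline summary that the protocol requires, declares neither omission in Section 9, and keeps unscheduled tests out of summaries. The averaging footnote is ambiguous, with consequences from no dilution to 4.9x shown as 1.56x; that last figure assumes the other six panels sit at 1x, and dilution is milder if they do not.

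The size is minor. Four patients were dosed, two per cohort, and every value is listed. The residual gap is a short rise in AST below 5x ULN, ALP or bilirubin that meets no DILI criterion and is not judged an adverse event. It would be wrong to infer that data are lost or that a serious liver signal would be hidden: this is a weakness in what the tables show. Confidence is medium, because the TFL shells could resolve part of it.

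**What to change.** - **SAP 5.1:** state that laboratory values are not averaged across visit numbers.
- **SAP 7.9.2:** restore the graded summary as each patient's worst post-baseline CTCAE grade, or worst multiple of ULN and of baseline, over scheduled and unscheduled tests. Specify the change-from-baseline summary. If either is deliberately dropped, declare it in Section 9 beside the shift tables.
- **Source:** use central results, as the protocol says. If local results are used where no central one exists, flag them by source and declare the departure in Section 9. Table 18 plans both a central and a local panel at V2, so each source has its own baseline.

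The cost is some SAP wording, possibly a Section 9 entry, and one or two extra tables for 4 patients. Central and local liver results are both already captured electronically (Protocol 8.1.12). If local values are used, the drawback is mixed reference ranges.

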5.2 Data Handling Rules

Missing Data

No imputation for missing data will be carried out.

Partial Date Imputation

Detailed rules for partial date imputation are described below.

General rules for Adverse events (AE) and prior and concomitant medications (CM)

- In case of partial dates with missing day:

For AE and CM, any partial start date during the month of VTX-801 dosing will be imputed to be the date of VTX-801 dosing, taking the worst-case scenario.

For any AE and CM starting after the month of VTX-801 dosing, the start date will be imputed to be the first day of the month.

For any AE and CM starting before the month of VTX-801 dosing, the start date will be imputed to be the last day of the month.

Partial AE and CM end dates will be imputed to be the last day of the month or at the date of study discontinuation/completion, whichever occurs first.

- In case of partial dates with missing day and missing month:

For AE and CM, any partial start date during the year of VTX-801 dosing will be imputed to be the date of VTX-801 dosing, taking the worst-case scenario.

For any AE and CM starting after the year of VTX-801 dosing, the start date will be imputed to be the first day of the year (e.g., 01 January).

For any AE and CM started before the year of VTX-801 dosing, the start date will be imputed to be the last day of the year (e.g., 31 December).

Partial AE and CM end dates will be imputed to be the last day of year (e.g., 31 December) or at the date of study discontinuation/completion, whichever occurs first.

Some examples are given below (DDMMYYYY).

In most cases, start dates are imputed as first day of the month or first day of the year.

Table 1: Examples of missing dates imputation

Data Type	Start Date	Imputed Start Date	First Study Treatment Dose Date	End Date	Imputed End Date
Adverse Event, Prior/ Concomitant Medication	JAN2017	31JAN2017	11NOV2017	MAR2017	31MAR2017
	MAR2017	01MAR2017	27JAN2017	MAR2017	31MAR2017
	2017	27JAN2017	27JAN2017	2017	16MAR2017 ^f
	MAR2017	01MAR2017	27JAN2017	MAR2017	01MAR2017*
	JAN2017	31JAN2017	27FEB2017	2017	31DEC2017
	2016	01JAN2016	27FEB2017	SEP2016	30SEP2016

^f Patient discontinued on 16MAR2017; * Patient discontinued on 01MAR2017.

Rules for other partial dates

If partial date is present for dates related to disease history, the same rules as for AE and CM will be applied.

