11.4.4.1 Adverse Events

AEs will be coded using the Medical Dictionary for Regulatory Activities (MedDRA). System Organ Class (SOC), High-Level Group Term (HLGT), High Level Term (HLT), Preferred Term (PT), and Lower-Level Term (LLT) will be attached to the clinical database.

AEs will be summarized based on the date of onset for the event. Summaries (number and percentage of patients) of treatment-emergent AEs will be provided by SOC and PT, by dose cohort and overall.

Treatment-emergent adverse event is defined as any AE that emerges during or after IMP administration having been absent pre-treatment or worsens relative to the pre-treatment state.

Events that are considered possibly, probably or definitely related to the IMP, deaths, SAEs, and AEs resulting in IMP discontinuation will also be tabulated by SOC and PT.

A tabulation will also be provided that summarizes at least treatment-emergent and treatment-related AEs (possibly, probably or definitely related) by maximum severity (i.e., CTCAE grade).

Duration of AEs will also be investigated as appropriate.

All AEs, including treatment-emergent and non-treatment-emergent AEs, will be listed in patient data listings.

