7.6 Prior and Concomitant Medications

Prior and concomitant medications will be coded using WHOHD dictionary.

Medications will be defined as follows:

- Prior Medication: any medications with start date before VTX-801 dosing.
- Concomitant Medication: any medications with end date either the same or after VTX-801 dosing or missing.

Any medications with start date before the first study treatment date and end date either after the first study treatment date or missing will be assumed to be both prior and concomitant medication.

The number and percentage of patients with prior and concomitant medications will be tabulated by cohort and overall, by Anatomical Therapeutic Chemical Classification (ATC) and preferred term (PT) on the SAF. A by-patient listing will be produced for prior and concomitant medications as well as for all prior therapies.

Prior and concomitant medications attached to WD will be listed.

Surgery and Medical Procedures:

Surgery and Medical Procedures will be listed on the SAF.

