7.9.1 Adverse Events

Adverse events (AEs) will be coded using MedDRA dictionary.

AEs will be graded according to the National Cancer Institute – Common Terminology Criteria for Adverse Events (NCI-CTCAE) version 5, based on study protocol.

The following definitions will be used:

- Treatment-emergent AEs (TEAEs): AEs that occurred during on-treatment period, from the day of VTX-801 dosing,
- Related AEs: AEs suspected by the Investigator to have a relationship to study treatment (as recorded on the AE eCRF page, Relationship to VTX-801 = Possibly related, Probably related, Definitely related or missing,
- Serious Adverse Events (SAE): serious AEs (as recorded on the AE eCRF page, Does AE Meet the Definition of an SAE = Yes),
- AEs leading to Death: adverse event leading to death (as recorded on the AE eCRF page, Results in death, or Outcome = Fatal, or Grade = 5),
- Liver function AEs: adverse event meeting the definition of a suspected DILI (as recorded on the AE eCRF page, does AE meet the definition of a suspected DILI event? = Yes).

An overview summary table will present the number and percentage of patients with a TEAE, including:

- TEAEs / TEAEs related to study treatment,
- Serious TEAEs / Serious TEAEs related to study treatment,
- Liver TEAEs / Liver TEAEs related to study treatment,

- Adverse events of special interest (AESI) / AESI related to study treatment,
- Dose Limiting Toxicity / Dose Limiting Toxicity related to study treatment,
- TEAEs leading to death / TEAEs related to study treatment leading to death,
- TEAEs with NCI-CTCAE grade ≥ 3 / TEAEs related to study treatment with NCI-CTCAE grade ≥ 3 ,
- TEAE meeting any stopping rule,
- TEAE Related to Radiocopper Administration,
- TEAE related to Other Study Procedure.

In addition, the following tables will be produced by SOC and PT:

- TEAEs / TEAEs related to study treatment,
- Serious TEAEs / Serious TEAEs related to study treatment,
- Liver TEAEs / Liver TEAEs related to study treatment,
- TEAEs and maximum CTCAE grade / TEAEs related to study treatment and maximum CTCAE grade,
- TEAEs leading to death / TEAEs related to study treatment leading to death,
- Non-serious TEAE.

A patient with multiple occurrences of an AE will be counted only once in the AE category. SOCs will be sorted by descending order of frequency for the overall group, PTs will be sorted by descending order of frequency for the overall group within each SOC.

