All deaths and on-treatment deaths will be listed together with the corresponding reasons.

The following listings will be provided:

- All AEs, identifying events collected during the pre-treatment and on-treatment,
- Serious AE,
- Non-Serious AE.

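### SAP 5.2 moves partial start dates to the dosing date without checking the end date, so an event over before dosing can start after its own end and count as a TEAE

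*SAP*

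**What the plan says.** SAP 5.2 (Partial Date Imputation) has two rules that send a start date to the dosing date. With the day missing, "any partial start date during the month of VTX-801 dosing will be imputed to be the date of VTX-801 dosing, taking the worst-case scenario". With day and month missing, "any partial start date during the year of VTX-801 dosing will be imputed to be the date of VTX-801 dosing". End dates are handled separately: "Partial AE and CM end dates will be imputed to be the last day of the month", or to 31 December when the month is missing too, with study discontinuation or completion used if earlier. Nothing compares the two results.

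The imputed dates feed these definitions:

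- SAP 7.9.1 defines TEAEs as "AEs that occurred during on-treatment period, from the day of VTX-801 dosing".
- Protocol 11.4.4.1 states "AEs will be summarized based on the date of onset for the event" and defines a TEAE as "any AE that emerges during or after IMP administration having been absent pre-treatment or worsens relative to the pre-treatment state".
- SAP 7.9.1 also plans a listing of "All AEs, identifying events collected during the pre-treatment and on-treatment".
- SAP 7.6 defines prior medication as "any medications with start date before VTX-801 dosing". Concomitant medication is one whose end is missing or falls on or after dosing.

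**The concern.** Choosing the dosing date as a worst case is sensible when it is unknown whether an event began before or after the infusion. It is not sensible when the end date already shows that the event was over. The rule then produces an impossible record and, if the flag is taken from the imputed start, a TEAE that the protocol's definition excludes.

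TEAEs are part of the primary endpoint, and SAP 8.1 makes safety the focus of the abbreviated report. Events that begin and end before dosing are in the data by design: protocol 9.2.6 (Table 16) captures all AEs from Screening 2 onwards, and sirolimus and the first radiocopper injection fall in the week before infusion. The AE listing lets a reader inspect single events, but its pre-treatment or on-treatment label carries the same error if it is derived from the imputed start.

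**Working it through.** **Step 1. Reproduce the SAP's examples.** Applying the written rules of SAP 5.2 to the six rows of its examples table:

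| Row | Start | Dose | End | Rule gives (start / end) | Table shows (start / end) |
|---|---|---|---|---|---|
| 1 | JAN2017 | 11NOV2017 | MAR2017 | 31JAN2017 / 31MAR2017 | same |
| 2 | MAR2017 | 27JAN2017 | MAR2017 | 01MAR2017 / 31MAR2017 | same |
| 3 | 2017 | 27JAN2017 | 2017, discontinued 16MAR2017 | 27JAN2017 / 16MAR2017 | same |
| 4 | MAR2017 | 27JAN2017 | MAR2017, discontinued 01MAR2017 | 01MAR2017 / 01MAR2017 | same |
| 5 | JAN2017 | 27FEB2017 | 2017 | 31JAN2017 / 31DEC2017 | same |
| 6 | 2016 | 27FEB2017 | SEP2016 | **31DEC2016** / 30SEP2016 | **01JAN2016** / 30SEP2016 |

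Five rows reproduce in full. Only row 3 uses the dosing-date rule, and its end is after dosing, so the table never exercises the problem case.

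**Step 2. Apply the rule to records that ended before dosing.** These are constructed records using dose dates from the table.

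- Month rule: dose 27JAN2017, start JAN2017, end 15JAN2017. Imputed start = 27JAN2017. Start minus end = 27 − 15 = 12 days.
- Year rule: dose 27FEB2017, start 2017, end JAN2017. Imputed end = 31JAN2017; imputed start = 27FEB2017. Start minus end = 27 days. The imputed end is Day −27. For this dose the nominal Screening 2 window (Day −49 to Day −14) runs from 09JAN2017 to 13FEB2017, so the imputed end falls inside it.

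**Step 3. Classify them.**

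- As AEs: the imputed start equals the dosing date, so a test of start on or after dosing makes both TEAEs. Under the protocol's definition neither qualifies, because neither emerged or worsened during or after the infusion.
- As medications: the start is not before dosing, so not prior; the end is before dosing, so not concomitant. Both fall outside the two classes of SAP 7.6.

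**Step 4. Find where the problem stops.** If the end is also known only to the dosing month, SAP 5.2 sets it to month end (or discontinuation, if earlier) and no conflict arises. For example, start NOV2017, end NOV2017 and dose 20NOV2017 give 20NOV2017 to 30NOV2017. The month rule therefore fails only with a complete end date before dosing; the year rule also fails when the end is known only to an earlier month.

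**Step 5. Size.** SAP section 9 gives 2 patients in each of cohorts 1 and 2, 4 in total. One false TEAE moves a row by at most 1/2 = 50 percentage points in a cohort or 1/4 = 25 overall, and only if that patient has no other TEAE in that row.

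**Step 6. Row 6 (a separate, minor point).** The rule for years before dosing gives 31DEC2016, which is 92 days after that row's imputed end of 30SEP2016; the table shows 01JAN2016. No TEAE or prior/concomitant flag changes, since both dates precede dosing. SAP 5.2 applies the same rules to disease-history dates, however, so for a diagnosis known only to the year, time since diagnosis (SAP 7.4) differs by 31DEC2016 − 01JAN2016 = 365 days (364 in a non-leap year) depending on which version is programmed. The sentence above the table, that starts mostly go to the first day of the month or year, fits rows 2, 4 and 6, or only rows 2 and 4 if row 6 follows the rule.

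**The case against.** The strongest reply is that the miscounting is conditional. The SAP does not say outright that the TEAE flag uses the imputed start, and an event with a recorded end before dosing did not occur in the on-treatment period on any plain reading. That stands as a limit: the impossible dates are certain, the false TEAE is not. But summaries are by onset date, and calling the dosing date a worst case only makes sense if the imputed start decides the flag.

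A second reply is rarity. There are 4 dosed patients, and protocol 12.4.1 and 12.4.3 provide data checks and queries. Rarity is conceded. The checks do not remove the problem, though: a raw start of JAN2017 is consistent with an end of 15JAN2017, and the conflict appears only at imputation.

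Third, the year-rule example is less natural than the month-rule one. It needs an AE dated only to the year at onset but to the month at its end. A true end in the first eight days of January would also precede the nominal Screening 2 window, when only procedure-related AEs are captured. The month-rule case is the stronger of the two.

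Fourth, the consequences are bounded. The analysis is descriptive, all AEs are listed, the error only over-counts, and an event resolved before dosing should normally be judged unrelated to VTX-801, so related-TEAE rows are largely protected. No endpoint depends on the medication classes. All of this is fair and limits the effect. It does not make the rule correct. Likewise, the first-day sentence may describe expected data rather than the six rows, so the count of rows is weak evidence; the contradiction in row 6 remains.

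**Conclusion.** The concern holds. As written, SAP 5.2 gives a start later than the end for any record whose start is known only to the dosing month or year and whose end, recorded or imputed, is before dosing: 12 and 27 days in the two examples. Under SAP 7.6 a medication with those imputed dates belongs to neither class. An AE with those dates becomes a TEAE, against the protocol's definition, provided the flag is derived from the imputed start.

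The number of affected records is unknown and probably small. The 50- and 25-point figures are ceilings for one event, not estimates of the effect. The mismatch in row 6 is real but minor. The change should be made before the tables are run, because the rule bears on part of the primary endpoint and the correction is simple.

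**What to change.** In SAP 5.2, impute a partial start to the dosing date only when the end date is missing or the known or imputed end is on or after dosing. Otherwise set the start to the known or imputed end date, and classify the AE as pre-treatment (not a TEAE) or the medication as prior. Setting the start to the end date is one workable convention; what matters is that the start does not pass the end and that the record stays pre-dose.

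Applied to the examples, the month-rule record starts on 15JAN2017 and the year-rule record on 31JAN2017. Both become pre-treatment or prior. The record in Step 4, whose imputed end is after dosing, keeps the dosing date and remains a TEAE, so the worst-case intent is preserved.

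Also make the rule for years before dosing, row 6 and the first-day sentence follow one convention, with the start capped at the end date.

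The cost is a few lines of SAP text, one example cell and one added condition in the imputation program.
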